- Arm 1: Treatment as Usual (TAU) control: A “usual care” control group (e.g., antidepressants, watchful waiting, psychosocial therapy, or no treatment, all determined by the participant in consultation with their TAU providers). All TAU will be recorded for all participants in all study conditions; or
- Arm 2: TAU + Minimal BLT Encouragement: TAU plus two minimal communications (mailed letter, secure EHR message, email, or text) identifying BLT as a promising treatment and outlining steps for participants to self-initiate. Arm 2 will not include any phone coaching or adherence promotion.
- Arm 3: TAU + Enhanced BLT Encouragement + Adherence Promotion + MI: TAU plus 2-6 brief calls to encourage BLT use, advise on purchase of a light box (LB) that meets all ideal technical

standards, assist with obtaining compensation for LB purchase, educate for correct LB use, and provide motivational interviewing (MI) as needed to promote adherence.

Outcomes will be assessed at baseline, 2, 4, and 6 months. The acute intervention period will be for 2 months. The primary outcome will be scores on the Patient Health Questionnaire-9 (PHQ-9), selected as representative of how depression is assessed in many usual care settings, consistent with effectiveness research principles.

5. Study Population

a. Number of Subjects

We will enroll 90 to 100 participants.

b. Inclusion and Exclusion Criteria

Potentially eligible individuals will be screened at two points in the recruitment phase: 1) preliminary identification of likely participants via a search of KPNW electronic health record (EHR) and 2) phone or online screening survey.

EHR inclusion criteria:

- Age 18-69 years, inclusive, and
- New episode of unipolar depression within the last month, defined as: New ICD-10 diagnosis of SAD or unipolar depression (i.e., major depression, minor depression, depression not otherwise specified, and/or adjustment disorder with depressed mood) AND usual care administration of the PHQ-9 depression scale in the last 30 days, with a total score of 10 or higher, and
- Participant must have a kp.org MyChart account, with evidence of use in the last 12 months.

EHR exclusion criteria:

- Chronic depression: ICD-10 diagnosis of SAD or unipolar depression in the 6 months prior to case-identification;
- Elevated PHQ-9 (score of 10 or higher) in the 6 months prior to case identification.

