A request for Waiver of Authorization is also requested for recruitment. During the first stage of the screening process, we will run an EHR case-finding program to generate an initial outreach list of potentially eligible individuals. This initial case finding algorithm does not itself qualify individuals for the study, but merely generates a likely pool within which further screening is merited.

This waiver allows study staff to approach (via letter, email/the EHR patient portal, and subsequent phone call) likely interested and eligible individuals and offer them the study opportunity. The study could not complete the research without access to and use of PHI because it is not practical to recruit eligible individuals without pre-identifying using medical record information and contact information. It would be too costly and would un-duly burden the KP membership to receive invitations to every study. Only the minimum amount of PHI will be accessed to identify participants who are likely to meet the study eligibility criteria.

6. Study Procedures

Recruitment

Recruitment procedures are described in the earlier Recruitment Methods section.

Randomization

Participants will be randomized 1:1:1 to three conditions, stratified by gender (male vs. female + all non-CIS gender identities), age (median split; estimated as <46yrs vs >= 47yrs), and minority status (white non-Hispanic vs. all other races/ethnicities).

Monitoring for Safety

The target condition is depression, and the most likely emergent risks (and how we will monitor for these) are:

- Worsening depression, evaluated at each assessment with the PHQ-9 depression measure.
- Intentional self-harm, including suicidal thoughts and behavior. This will be evaluated at each assessment with the Columbia Suicide Severity Rating Scale (C-SSRS).
- Emergent bipolar disorder symptoms (a possible risk of triggered symptoms from lightbox use). This will be assessed at each follow up assessment with the 5-item Altman Self-Rating Mania Scale (ASRM).

Any increased risk evident from any of these measures, or other unexpected increased in other less common safety issues (e.g., threats to harm others) will be reviewed between the interviewing staff and [name], with a review of the relevant usual health care the individual is already receiving.

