Arm 2: TAU + Minimal BLT promotion. Participants will receive 2 brief communications (mailed letter, secure EHR message, email, and/or text) identifying BLT as a promising treatment with few side effects, and steps for participants to self-initiate. The educational and background information from the 2 communications will also be made available as PDFs or webpages on the secure study website. If requested, participants will be provided with a copy of these materials by email. Arm 2 has no phone coaching, adherence promotion or MI.

Arm 3: TAU + BLT encouragement + adherence promotion. BLT promotion coaches will follow a four-

step approach in engaging with Arm 3 participants: (a) provide encouragement to consider using BLT; (b) provide guidance regarding light box purchase and compensation; (c) educate participants about ideal BLT use to obtain maximum benefit; and (d) provide ongoing brief telephonic adherence promotion and motivational interviewing (MI) where warranted to maximize persistent and appropriate BLT use. The educational and instructional information for these 4 steps will also be made available as PDFs or webpages on the secure study website. If requested, participants will be provided with a copy of these materials by email.

Encouragement. Coaches will encourage participants to consider BLT during the first post-randomization contact, in most cases by telephone. Coaches will address the reason for the call (BLT promotion) and advantages of BLT. They will also gauge interest in using BLT; for ambivalent participants they will offer a brief motivational interviewing (MI) exercise.

Compensation for BLT purchase. In Arms 2 + 3 interested participants will receive written guidance on purchasing a light box (LB) that meets minimum study requirements. Arm 3 coaches guide participants to purchase LBs and obtain compensation (up to \$80 in Fred Meyer gift cards) for this cost through the study. This compensation process is modeled to simulate the KP durable medical equipment (DME) benefit, which does not currently cover LBs. Arm 2 offers the same written information about LB purchase and compensation, but no coach assistance.

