National Database for Autism Research (NDAR) We will share de-identified participant data with the National Institute of Mental Health Data Archive (NDA) as required by the NOA.	 Fully Identifiable  Limited Data Set  De-Identified  Aggregate	 Yes  No	 Signed Authorization  Waiver of Authorization  Limited Data Set only (DUA Required)  De-Identified or Aggregate Data  N/A, No Health Information

8. Provisions to Monitor Data to Ensure the Safety of Subjects

[name] will assume responsibility for and oversee patient safety on the overall project. Drs. [name] and [name] will liaise with a data safety monitoring board (DSMB), which will have overall review responsibility for patient safety and serve as a reporting body to the NIMH and study IRB. The DSMB will consist of 3 TBN members: a community mental health advocate, a biostatistician, and another clinical or research mental health expert.

The DSMB will conduct twice-yearly reviews to determine whether patient safety has been adequately safeguarded. The DSMB members, in consultation with [name], are empowered to take whatever immediate action is necessary to safeguard the welfare of individual patients. The DSMB group will also examine adverse events (AEs) annually, and serious adverse events (SAEs) as they occur (see reporting times below). Safety information will be collected at each assessment timepoint as described previously in section 6 under "Monitoring for Safety".

[name] will generate quarterly interim reports for the DSMB as well as summary 6-month reports. These interim analyses will be conducted for safety outcomes (suicidal behavior, other crises, study terminations, all AEs, SAEs, other events) and data quality indicators (recruitment, retention, instrument reliability, intervention fidelity), but not routinely for clinical effectiveness or economic outcomes. Study conditions will be masked (e.g., Red, Green, Blue arms) in these safety and data quality reports but the DSMB can request unblinding at its discretion should a safety or data quality concern arise.

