The study team will notify the IRB and the DSMB (and as required, the NIMH Project Officer) of any clinically significant new emergent issues detected in this study, even if seemingly unrelated to the study, BLT or procedures (e.g., new diagnosis of cancer). We will follow KPNW IRB reporting dates for DSMB notification. In many cases, because the study does not routinely assess participants for new emergent issues that are not anticipated as a possible risk (see list of expected clinical issues in section 6 under "Monitoring for Safety"), these incidental diagnoses/conditions will be detected either through spontaneous patient report or review of the electronic health record (EHR). Given that all participants are members of the Kaiser Permanente health organization, in the case of new EHR-recorded diagnoses/conditions this means that the usual care health providers (primary care providers, mental health and other specialists) will already know about and will be addressing these conditions/diagnoses.

Given the enrolled population will have been pre-identified by virtue of EHR depression clinical diagnosis or elevated PHQ-9, none of the clinical events summarized previously (worsening depression, suicide/self-harm, new comorbidity, Bipolar Disorder) are considered 'unexpected.' In other words, they are not unusual given the high comorbidity of depression with other mental disorders generally. Suicide, self-harm, anxiety, substance misuse and BD are particularly possible given the case-selection for active depression disorder and/or symptomatology. In this study, the most likely anticipated event possibly related to research would be the precipitation of BD and any variant on exposure to BLT. We will make appropriate clinical referrals to emergency or non-emergency services, and/or communicate with TAU providers as warranted – and as summarized previously.

9. Risks and Benefits

a. Risks to Subjects

The assessments and treatments in this study pose no greater risk than standard treatment or therapy, or clinical interviews. These risks include:

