1. The potential for an unintended breach of confidentiality. We will be in touch with participants by email and text message to schedule study events or to remind them about surveys. Any confidential information sent through the Internet or by text message has a small risk of being read by someone other than the person it was sent to. As described in the data handling section above, we will store all information in locked cabinets, on password protected servers, or within REDCap (a HIPAA-compliant, web-based application for data capture).
2. The possibility of distress in association with addressing emotional difficulties during the completion of surveys or study activities. Participants are free to refuse to answer any questions and will be reminded of this prior to addressing sensitive subjects.
3. Engaging in bright light therapy may have risks for individuals with vulnerability to phototoxicity, photosensitive skin, or who are taking a photosensitizing medication or herb. Our EHR case-finding program will exclude patients with active EHR diagnoses and prescriptions representing any of the few contraindications for BLT. We will also ask about these diagnoses and conditions during the screening survey to further exclude those with these potential contraindications.
4. There is a small risk of manic activation from BLT light exposure. This risk is inherent in the general population and could occur whether or not individuals were enrolled in the study. Our EHR case-finding program will exclude patients with any variation of bipolar disorder recorded in the EHR. We will also screen for emerging symptoms of mania during the screening survey and follow-ups. We will inform the TAU providers of our participants that their patients are participating in this study, which may involve self-administration of BLT. If study staff suspects a participant is in danger or unsafe, they will immediately report this to a licensed study team member and discuss possible strategies for responding (see DSMP section for more details).

Some participants may become pregnant during the study. However, nothing in the study procedures or interventions is expected to have any adverse impact on the mother or child.

b. Potential Benefits to Subjects

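### No named instrument asks about light-exposure side effects and only Arm 3 has coach calls, so minor unsolicited events will be captured unequally by arm

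*Protocol*

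**What the plan says.** **What is solicited.** Protocol section 6 (Monitoring for Safety) names three emergent risks, each with one scale: PHQ-9 for worsening depression, C-SSRS for self-harm and ASRM for mania. On the last it says "This will be assessed at each follow up assessment with the 5-item Altman Self-Rating Mania Scale (ASRM"). Section 8 defines safety collection at each timepoint by pointing back to this list. Section 4 sets the timepoints: "Outcomes will be assessed at baseline, 2, 4, and 6 months".

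**What is anticipated.** Section 3 expects light therapy to cause side effects, mostly minor and short-lived. Section 9.a states "Engaging in bright light therapy may have risks for individuals with vulnerability to phototoxicity, photosensitive skin", and lists manic activation as a separate risk.

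**What happens off the list.** Section 8, on emergent issues that were not anticipated: "these incidental diagnoses/conditions will be detected either through spontaneous patient report or review of the electronic health record (EHR").

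**Who is in conversation with the study.** Section 4 gives Arm 3 two to six coach calls. Section 6 has coaches take up reactions and discomfort during those calls, with an intervention contact form used in that arm only. For the other light-therapy arm, "Arm 2 has no phone coaching, adherence promotion or MI".

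**What is reported.** Section 8 sends the DSMB regular reports, under masked arm labels, covering "suicidal behavior, other crises, study terminations, all AEs, SAEs, other events". None of the SAP sections available covers safety.

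**The concern.** Two arms are encouraged to use the same kind of light box, but only one of them regularly talks to a person about how it feels. A sore eye or a headache that never reaches a clinic is likely to be mentioned in an Arm 3 call. In Arm 2 it would be recorded only if the participant volunteered it, or if some unspecified survey item happened to ask.

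The masked DSMB tables would then show more minor events in Arm 3 even if the two arms tolerated the device equally well. An imbalance of that kind could prompt a needless request to unblind, or a real imbalance could be dismissed as an artefact. The pilot exists to prepare a full trial, and it would pass on a tolerability figure that cannot be read by arm. Arm 1, which should supply the background rate of headaches and the like, has no matching question either.

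**Working it through.** The plan gives no adverse event rate, so there is no figure to reproduce. The check has two parts.

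**1. Collection routes by arm (protocol section 6)**

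| Route | Arm 1 | Arm 2 | Arm 3 | Asks about light reactions? |
|---|---|---|---|---|
| PHQ-9, C-SSRS, ASRM | yes | yes | yes | No: depression, self-harm, mania |
| Other listed survey measures | yes | yes | yes | None named |
| EMA | yes | yes | yes | Described as mood and sleep; adherence added in Arms 2 and 3 |
| Month-2 satisfaction and feedback | no | yes | yes | Items not shown |
| Coach calls and contact form | no | no | yes | Reactions and discomfort discussed |
| Exit interviews, 12 to 16 people | some | some | some | Having reported side effects is a selection trait (Arms 2 and 3) |
| EHR | yes | yes | yes | Only what reaches a provider; study messages to providers go out for Arms 2 and 3 only |

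Total contact is largely shared. EMA alone gives up to 4 × 9 + 2 × 17 = 36 + 34 = 70 prompts per participant in every arm, taking 26 weeks in all. The difference is narrower: who is in live conversation about reactions to light. Within Arm 3 it may also depend on tolerability. Section 6 treats discomfort as a barrier to adherence and gives weakly adherent participants more contacts.

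**2. What unequal capture does to the counts**

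From the documents: "We will enroll 90 to 100 participants" and "Participants will be randomized 1:1:1 to three conditions", so n = 90/3 = 30 per arm at the minimum. All rates below are assumptions.

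Let u be the proportion using a light box, s the side-effect probability among users (the same in both arms) and c the probability that an event is recorded.

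- Expected recorded events = n × u × s × c
- Arm 3 to Arm 2 ratio = (u3 × c3)/(u2 × c2), since n and s cancel

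*Equal true rates.* If u × s = 0.30 in both arms, each has 30 × 0.30 = 9 true events.

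- Arm 2, capture 10-30%: 0.9 to 2.7 recorded
- Arm 3, capture 50-80%: 4.5 to 7.2 recorded
- Ratio: lowest 4.5/2.7 = 1.7, highest 7.2/0.9 = 8

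*Equal use, stated explicitly.* With u = 0.5 and s = 0.2, each arm has 30 × 0.5 × 0.2 = 3.0 true events.

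- Arm 3 at 80% capture: 2.4
- Arm 2 at 30-50% capture: 0.9 to 1.5
- Ratio: 2.4/1.5 = 1.6 to 2.4/0.9 = 2.7
- At 80% capture in both: 2.4/2.4 = 1.0

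*Unequal use.* With u2 = 0.3, u3 = 0.7 and s = 0.2, true events are 1.8 and 4.2, a real ratio of 0.7/0.3 = 2.33.

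- Same capture rates as the previous case: 0.56/0.15 = 3.7 to 0.56/0.09 = 6.2
- Equal capture: back to 2.33

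In the last case part of the excess is real and part is capture, and the planned data could not separate them.

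**The case against.** The strongest reply is that the gap is smaller than it looks. Several parts of it stand.

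- **The section 8 sentence is about something else.** It concerns incidental conditions that were not anticipated, whereas light reactions are. A reader might infer that the protocol assigns them to spontaneous report; it does not say so. They end up there only because they are absent from the section 6 list and no other route common to all arms is given.
- **The questions may exist.** The assessment scripts are in a separate document, and the month-2 feedback items for Arms 2 and 3 are not shown. Exit interviewees may be picked partly on survey responses, which suggests that some survey could pick up side effects. So it cannot be claimed that side effects are never asked about, only that no named instrument does so. Even a feedback survey that did ask would omit Arm 1 and months 4 and 6.
- **People vulnerable to phototoxicity are excluded twice,** by EHR search and by screening survey. That lowers the expected rate of serious reactions. It does not measure the minor ones expected in section 3.
- **Arm 3 is designed to increase use,** so more side effects there may be genuine.
- **The DSMB reports are not a planned between-arm test,** and a tolerability rate is not among the pilot deliverables in section 2. This limits the importance of the point, but the tables will still be shown by arm.

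A reader might also infer that mania goes unscored until month 2. The Survey Measures text gives all listed scales, ASRM included, at baseline and every follow-up, and screening asks about manic symptoms. Month 2 is only the first score after randomization. Arms 2 and 3 also receive written information on recognising mania, and their providers are alerted to emergent bipolar disorder. An extra ASRM during the acute phase would be a monitoring preference, not the repair of a defect.

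**Conclusion.** The point holds in a limited form. Unsolicited, mainly minor, events will be captured unequally between Arm 3 and the other arms, so the masked-arm adverse event tables will mix coach contact with light box use.

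It would be tempting to conclude that adverse event rates will reflect contact instead of light therapy. The documents do not support that. Worsening depression, suicidality and mania are solicited identically in all arms, with interviewers blinded to condition, and are not affected. For the remaining events, contact is confounded with use and does not replace it.

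The size cannot be fixed from the documents. With equal true rates it equals the ratio of the capture rates: 1.7 to 8 under one set of assumed capture rates and 1.6 to 2.7 under another. These figures show the mechanism and are not estimates. The conclusion also assumes that the unseen survey items do not already include a side-effect checklist common to all arms. The remedy is a cheap improvement.

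**What to change.** 1. Add one short fixed side-effect checklist (eye, skin, headache and similar), worded without reference to light therapy, to the existing 2-, 4- and 6-month REDCap surveys in all three arms.
2. State in the SAP that any between-arm tolerability comparison rests on this checklist. Tabulate coach-reported and other spontaneous events separately by arm, and present rates alongside light box use.
3. Reconcile protocol section 6 (Monitoring for Safety and Survey Measures) with sections 8 and 9.a, so that the measured risks match the named risks and the ASRM schedule, baseline plus each follow-up, is stated the same way throughout.

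The cost is a small protocol and form amendment, a few more survey items per participant and more minor events to tabulate. No new visits or staff are needed, and the handling of any reported symptom is unchanged. If the unseen survey items already contain such a checklist in all arms, it is enough to name it in the protocol and add the SAP text.

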## SAP Revision History

Version edited	Date edited	Section number changed	Description and reason for change

# INTRODUCTION

This statistical analysis plan provides guidelines for the final presentation and analysis for the BLT Pilot Trial. The R34 pilot was designed to prepare for a future, fully-powered effectiveness trial. This study collects information to conduct the BLT Pilot Trial as described in these following aims:

Aim 1.1: We will enroll 90 depressed patients in this modest-size feasibility pilot, and randomize them to:

- Arm 1: Treatment as Usual (TAU) control: A “usual care” control group (e.g., antidepressants, watchful waiting, psychosocial therapy; all TAU will be recorded for all participants in all study conditions); or
- Arm 2: TAU + Minimal BLT Encouragement: TAU plus two minimal communications (mailed letter, secure EHR message) identifying BLT as a promising treatment, and outlining steps for patients to self-initiate. Arm 2 will not include any phone coaching or adherence promotion.
- Arm 3: TAU + Enhanced BLT Encouragement + Adherence Promotion + MI: TAU plus 2-4 brief calls to encourage BLT use, advise on purchase of a light box (LB), assist with obtaining insurance reimbursement, educate for correct LB use, and provide motivational interviewing (MI) as needed to promote adherence.

Aim 2. This small pilot sample is insufficient for confirmatory tests. However, we will conduct analyses that mirror those planned for a future, fully-powered trial. Key analytic contrasts are (a) active Arms 2 + 3 vs. control Arm 1; (b) each active Arm (2, 3) separately vs. control Arm 1; and (c) Minimal Arm 2 vs. Enhanced Arm 3. For each contrast we will initially examine differences between study arms in pre-post change in proposed mediators in BLT and MI effects; followed by examination of differences in pre-post change in the primary (PHQ-9) and key secondary outcomes (see Assessment). We then examine candidate mediators (improved sleep, normalized circadian rhythm, increased physical activity, readiness for change) for mediating BLT and MI effects on depression. We will also examine moderation of BLT effects and subgroup outcome variation (e.g., receiving vs. not receiving TAU ADs). Pilot feasibility data will facilitate rapid launch of a future trial: estimated recruitment, retention, and adherence with BLT protocol; and a cautious estimate (with wide confidence intervals) of BLT effectiveness.

